6.5.3.4. Dose reductions

Applicable to avelumab. Dose reduction is defined as actual non-zero dose < 90% of the planned dose.

Applicable to axitinib and sunitinib. Dose reduction is defined as a change to a non-zero dose level lower than that planned in the protocol.

The number and percentage of patients with at least one dose reduction as well as a breakdown of dose reductions (1, 2, 3, ≥4) will be summarized.

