##### **5.4.6.1. Inpatient Axitinib Dose Escalation and Dose Reduction**

Axitinib inpatient dose increase to 7 and/or 10 mg in combination with avelumab is prohibited in France, as per Agence nationale de sécurité du médicaments et de produits de santé (ANSM) request.

In other countries, inpatient axitinib dose escalation is permitted up to 10 mg BID and may occur according to the criteria described below.

Patients who tolerate the current axitinib dose without Grade >2 axitinib-related adverse events for 2 consecutive weeks have the option to have their axitinib dose increased (one dose level increase at a time) as indicated in Table 1 (unless the patient's BP is >150/90 mm Hg or the patient is receiving antihypertensive medication). Particular attention should be provided to a patient's overall safety profile prior to implementing inpatient axitinib dose escalation.

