**Table 1. Axitinib Dose Levels**

Dose Level	Dose
+2	10 mg BID
+1	7 mg BID
Potential Starting Dose	5 mg BID
-1	3 mg BID
-2	2 mg BID

Patients will be monitored closely for toxicity, and axitinib treatment may be adjusted by dosing interruption with or without dose reduction as indicated in Table 3. Dosing interruption and/or dose reduction by 1, and if needed, 2 dose levels (one dose level decrease at a time) as indicated in Table 1 will be allowed depending on the type and severity of toxicity encountered. Management of patients requiring more than 2 dose reductions of axitinib (one dose level decrease at a time) should be discussed with the sponsor's medical monitor.

Patients who have undergone dose reduction may also undergo dose re-escalation back to the previous dose level at the discretion of the Investigator in the absence of Grade  $\geq 2$  non-hematologic treatment-related toxicity for at least 28 days.

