6.5.3. Study treatment compliance and exposure

The following analyses will be based on the safety analysis set by treatment arm.

Cycle definitions for study drugs that are administered in combination apply to all the study drugs in the combination. I.e., cycle is patient-dependent, rather than study-drug-dependent when study drugs are administered in combination.

For Cycle X, actual cycle start date for each patient is

- the earliest start date of dosing in the Cycle X day 1 visit CRF exposure page, if the patient received study treatment on that visit (i.e., any study drug with dose>0 at that visit)
- the first day of assessments in the Cycle X day 1 visit, if the patient did not receive study treatment on that visit (i.e., all study drugs had dose=0 at that visit). Use start date in the exposure page if available; if start date is not available then use date of collection of vital signs on Cycle X day 1 visit.

Actual cycle end date for each patient is,

- for all cycles X except the last cycle, actual cycle end date = actual cycle (X+1) start date – 1 day;
- for the last cycle, actual cycle end date = actual cycle start date + 42 – 1 day

Cycle duration (weeks) = (actual cycle end date – actual cycle start date + 1)/7

When summarizing exposure for each study drug, only cycles from first dose of study treatment until the last cycle with non-zero dose of study drug (Arm B) or at least one of the study drugs (Arm A) should be included.

Exposure will be summarized (per cycle and/or overall) as dose received (cumulative dose, actual dose intensity) and as dose received relative to intended dose (relative dose intensity [RDI]).

The derivations below are provided for the following:

- Avelumab administered as a 1-hour IV infusion at a dose of 10 mg/kg once every 2 weeks in 6-week cycles.
- Axitinib administered BID PO at a dose of 5 mg.
- Sunitinib administered 50 mg PO QD on Schedule 4/2.

Analysis of exposure will be based on the calculated actual dose levels:

- Avelumab - total dose / weight
- Axitinib - total dose
- Sunitinib - total dose.

Exposure and compliance will be summarized by cycle and overall for each study drug in each treatment arm.

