6.5.3.5. Dose escalations

Applicable to axitinib only. Dose escalation is defined as a change to a dose level higher than that planned in the protocol.

Number and percentage of patients with at least one dose escalation as well as a breakdown of dose escalations (1, 2, ≥3) will be summarized.

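### SAP 6.5.3.4 and 6.5.3.5 compare each new dose with the fixed protocol dose instead of the previous dose, so some axitinib and sunitinib dose changes are miscounted in the exposure tables

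*SAP*

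**What the plan says.** SAP 6.5.3.4, for axitinib and sunitinib: "Dose reduction is defined as a change to a non-zero dose level lower than that planned in the protocol". It reports the number of patients with at least one reduction, and "a breakdown of dose reductions (1, 2, 3, ≥4) will be summarized".

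SAP 6.5.3.5, for axitinib only: "Dose escalation is defined as a change to a dose level higher than that planned in the protocol". It reports patients with at least one escalation and a breakdown by 1, 2 and ≥3.

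The planned dose is set in SAP 6.5.3: "Axitinib administered BID PO at a dose of 5 mg". The relative dose intensity in SAP 6.5.3.2 uses the same fixed reference, with a denominator of 7 × 2 × 5 mg per week of exposure.

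The protocol foresees movement on both sides of that dose. Table 1 lists axitinib levels of 2, 3, 5, 7 and 10 mg BID. Section 5.4.6.1 says that outside France "axitinib dose escalation is permitted up to 10 mg BID". The text under Table 1 describes reductions as steps from the dose held, one level at a time, and adds: "Patients who have undergone dose reduction may also undergo dose re-escalation back to the previous dose level". Table 2 lists sunitinib levels of 50, 37.5 and 25 mg QD, and Section 5.4.6.2 permits re-escalation to the previous level.

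**The concern.** The SAP wording looks only at where a dose change ends, not at where it began. That works for a patient who starts at the planned dose and only steps down. It fails once a patient has been above the planned dose, or has been below it and is coming back up.

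At stake is whether the exposure tables describe dose modification correctly for titrated patients. The protocol treats a step from 10 to 7 mg or from 7 to 5 mg BID as a dose reduction. The SAP would file the first under escalations and leave the second out of both tables. Toxicity-driven reductions are also tabulated from the adverse event form, so the clinical study report could contain two axitinib reduction tables that disagree, with no explanation.

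**Working it through.** The plan states no figure to reproduce, so the check is to enumerate the possible moves.

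**Inputs.** Axitinib levels 2, 3, 5, 7, 10 mg BID (Protocol Table 1); planned dose 5 mg BID (SAP 6.5.3); sunitinib levels 50, 37.5, 25 mg QD (Protocol Table 2).

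**Rule as written.** New non-zero level < 5: reduction. New level > 5: escalation. New level = 5: neither.

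**One-level axitinib moves.** Five levels give 4 adjacent pairs, so 4 × 2 = 8 directed moves.

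| Move (mg BID) | SAP label | Actual change | Correct? |
|---|---|---|---|
| 5→7 | escalation | escalation | yes |
| 7→10 | escalation | escalation | yes |
| 10→7 | escalation | reduction | **no** |
| 7→5 | neither | reduction | **no** |
| 5→3 | reduction | reduction | yes |
| 3→2 | reduction | reduction | yes |
| 2→3 | reduction | re-escalation | **no** |
| 3→5 | neither | re-escalation | acceptable |

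Three of the 8 are wrong. The move 3→5 is accepted because the protocol keeps re-escalation apart from escalation above the starting dose, so its absence from the escalation table is defensible.

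**Sunitinib.** 50→37.5 and 37.5→25 are correctly labelled reductions. 25→37.5 ends below 50, so it is labelled a reduction although the dose rises. 37.5→50 gets no label, which is acceptable because escalation is not tabulated for sunitinib.

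**Effect along example dose paths** (R = reductions, E = escalations):

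| Path | SAP rule | Previous dose as reference |
|---|---|---|
| Axitinib 5→7→5 | R 0, E 1 | R 1, E 1 |
| Axitinib 5→7→10→7 | R 0, E 3 | R 1, E 2 |
| Axitinib 5→7→10→7→5 | R 0, E 3 | R 2, E 2 |
| Axitinib 5→7→10→7→5→3 | R 1, E 3 | R 3, E 2 |
| Axitinib 5→3→2→3→5 | R 3, E 0 | R 2, E 0, plus 2 re-escalations |
| Sunitinib 50→37.5→25→37.5 | R 3 | R 2, plus 1 re-escalation |

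**Patient-level rows.**
- At least one reduction: the first three paths give 0 under the SAP rule, so those patients are missing. The fourth patient is captured because the dose ends below 5 mg. A move 2→3 adds no false patient, because reaching 2 mg already required a step below 5 mg.
- At least one escalation: unaffected. A move 10→7 requires an earlier step above 5 mg, so that patient is already correctly counted.

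**Breakdowns.** The reduction counts can be too low (10→7, 7→5) or too high (2→3, and sunitinib 25→37.5). The escalation counts can only be too high (10→7).

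**The case against.** The strongest defence is that a fixed reference is a legitimate convention. It matches the relative dose intensity denominator, and the avelumab reduction rule in the same section is also set against the planned dose. Ever below and ever above the protocol dose are interpretable summaries. This stands for an ever/never summary under that label. It does not stand for counting successive changes, and no such convention makes a step from 10 to 7 mg an escalation. Reading the planned dose as the patient's currently prescribed level would repair some labels, but the SAP does not say this, and its exposure derivations use 5 mg BID throughout.

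The second defence is that tolerability is covered elsewhere. SAP 6.6.1 identifies adverse events leading to dose reduction from the action recorded on the adverse event form, with no 5 mg threshold, and 6.6.1.1 to 6.6.1.3 tabulate them. This stands: a toxicity-driven step from 10 to 7 or from 7 to 5 mg recorded as a reduction would appear there.

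Several stronger readings are tempting but go too far:
- **Half of all moves are wrong.** This needs 3→5 to be an error, which the protocol's separate use of re-escalation does not support. A share of possible moves is also not a share of patients or events.
- **Every reduction from an escalated dose is lost.** A change from 7 or 10 mg to below 5 mg is still counted as a reduction.
- **A move from 10 straight to 5 mg shows the problem.** The protocol describes reduction one level at a time, so this is not a standard step.
- **The safety profile of the combination would be misstated, or the comparison tilted towards it.** The missing patients can arise only with axitinib, since sunitinib starts at its top level. But the adverse-event-based tables remain, the reduction breakdown can err in either direction, and the documents give no titration frequency from which to size the effect.

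**Conclusion.** The point holds as a counting error in descriptive exposure tables. Applied literally, the rule mislabels 3 of 8 one-level axitinib moves and sunitinib re-escalation from 25 to 37.5 mg. It omits from the row for at least one reduction every axitinib patient who stepped down from an escalated dose without going below 5 mg BID, and it distorts the reduction and escalation breakdowns. The exposure table may then disagree with the adverse-event-based reduction tables.

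The row for at least one escalation, all efficacy results, alpha and power are unaffected.

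This rests on two assumptions: that the planned axitinib dose is 5 mg BID, as the SAP's exposure section states, and that programming follows the definitions as written. The number of patients affected depends on how many were titrated, which the documents do not give. It would be zero for the axitinib step-downs from 7 or 10 mg at French sites, where the protocol says "dose increase to 7 and/or 10 mg in combination with avelumab is prohibited in France". This is a minor point, worth correcting because the correction is cheap.

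**What to change.** In SAP 6.5.3.4, for axitinib and sunitinib, define a reduction as a change to a non-zero dose level below the last prior non-zero dose level. In SAP 6.5.3.5, for axitinib, define an escalation as a change above the prior level to a level above 5 mg BID. Report re-escalations after a reduction separately for both drugs, and state which category takes a return to 7 or 10 mg BID after a step-down, so that no move is counted twice. If ever below the protocol dose is also wanted, add it as its own row under that label. A footnote should say that the adverse-event-based tables use the action recorded on the form, and so need not match the exposure counts.

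The cost is a few sentences of SAP text and a small change to the derivation code. No new data are needed beyond the dose records already used for exposure. The change concerns counting only and takes no position on dosing.

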#### **5.4.2. Axitinib**

Axitinib will be administered orally BID at approximately the same time in the morning and evening on a continuous dosing schedule, ie, without a break in dosing in the absence of drug-related toxicity (see [Section 5.4.6](#)). Axitinib tablets are to be taken approximately 12 hours apart and may be administered without regard to meals. Tablets must not be crushed, split, or dissolved, and patients should be instructed to swallow the study medication whole without manipulation or chewing of the medication prior to swallowing.

A dosing card will be provided to the patients to provide guidance for the correct use of axitinib.

Patients must be instructed that if they miss a dose or vomit anytime after taking a dose, they must not "make it up" with an extra dose, but instead resume subsequent doses as prescribed.

Any missed dose may be taken late, up to 3 hours before the next scheduled dose of that day, otherwise, it should be skipped and dosing resumed with subsequent doses as prescribed. Patient must be instructed to record all doses (missed or vomited doses or extra doses) in a dosing diary supplied by the site. If doses are missed or vomited or if an extra dose is taken, this must be indicated in the source documents and CRFs.

Patients experiencing toxicity may require treatment adjustment or discontinuation according to the guidelines specified in Table 1 and Table 3.

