6.5.3.2. Exposure to axitinib

The dose level is calculated as actual dose administered (mg/day).

Intended duration of treatment with axitinib (weeks)=

$$(\text{last dose date of axitinib} - \text{first dose date of axitinib} + 1)/7$$

Duration of exposure to axitinib (weeks) =

$$(\text{last dose date of axitinib} - \text{first dose date of axitinib} + 1)/7$$

Cumulative dose is the sum of the actual doses of axitinib received in the study.

Actual Dose Intensity (DI)

- Overall actual DI (mg/week) = [overall cumulative dose (mg)] / [intended treatment duration (weeks)]

Relative Dose Intensity (RDI)

- RDI (%) = $100 \times [\text{overall cumulative dose}] / [\text{intended cumulative dose per week} \times \text{number of weeks from first dose of study drug to last dose of axitinib}]$
= $100 \times [\text{overall cumulative dose}] / [7 \times 2 \times 5 \times \text{duration of exposure to axitinib}]$

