6.5.3.6. Dose interruptions

Applicable to axitinib and sunitinib.

An interruption is defined a 0 mg dose administered on one or more days for axitinib or within the dosing period of a cycle for sunitinib. What follows defines how dose interruptions will be counted in the case of multiple dose interruptions.

- If an interruption occurs consecutively for at least two days due to the same reason, then it will be counted only once (example: If the actual dose on days 1-3 is 10 mg and actual dose on days 4-5 is 0 mg and dose interruption on days 4-5 is due to AE, then the total number of dose interruptions is 1).
- If an interruption occurs consecutively for at least two days due to different reasons, then it will be counted for each reason (example: If the actual dose on days 1-3 is 10 mg and actual dose on days 4-5 is 0 mg and dose interruption on day 4 is due to AE and dose interruption on day 5 is due to dosing error, then the total number of dose interruptions is 2).
- If an interruption occurs for more than one day due to the same reason, but the days are not consecutive, i.e. there is at least one dosing day in between, then each dose interruption will be counted as a different occurrence (example: If the actual dose on days 1, 3 and 5, is 10 mg and actual dose on days 2 and 4 is 0 mg, and dose interruptions on day 2 and 4 are both due to dosing error, the total number of dose interruptions is 2).

A dose interruption is not considered a dose reduction or a dose delay.

The number and percentage of patients with dose interruptions and the corresponding reasons will be summarized.

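### Axitinib dose reductions and escalations are counted from milligrams taken per day, so one skipped or extra tablet can be tabulated as a dose change, while a skipped sunitinib dose is an interruption

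*SAP*

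**What the plan says.** SAP 6.5.3 bases the exposure analysis on calculated actual dose levels and lists axitinib as total dose. For axitinib, SAP 6.5.3.2 states: "The dose level is calculated as actual dose administered (mg/day"). SAP 6.5.3.3 uses the same definition for sunitinib. Three counting rules follow.

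- Reductions, axitinib and sunitinib (6.5.3.4): "Dose reduction is defined as a change to a non-zero dose level lower than that planned in the protocol".
- Escalations, axitinib only (6.5.3.5): "Dose escalation is defined as a change to a dose level higher than that planned in the protocol".
- Interruptions (6.5.3.6): "An interruption is defined a 0 mg dose administered on one or more days for axitinib"; for sunitinib the zero dose must fall within the dosing period of the cycle. The section adds that an interruption does not count as a reduction.

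The rules for the oral drugs set no tolerance or minimum duration and do not require that the change was prescribed. Avelumab does have a tolerance in the same section: "Dose reduction is defined as actual non-zero dose < 90% of the planned dose". The worked examples in 6.5.3.6 use daily amounts of 10 mg and 0 mg and count single days attributed to dosing error.

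The lapses will be recorded. Protocol 5.4.2 says of axitinib: "If doses are missed or vomited or if an extra dose is taken, this must be indicated in the source documents and CRFs". Protocol 5.4.3 requires the same for sunitinib.

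**The concern.** Axitinib is taken twice a day and sunitinib once. If the dose level is the amount taken in a day, half a day's axitinib is a non-zero level below plan, whereas one missed sunitinib dose leaves nothing. The same lapse then appears as a reduction in Arm A and an interruption in Arm B.

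The protocol treats these as different things. Sections 5.4.6 and 5.4.6.1 describe dose reduction as a step between listed levels in response to toxicity. Section 8.4 classes giving less than 80% of the planned dose for other reasons as an underdose and handles it with medication errors. A 5 mg axitinib day is 50% of plan, so when it results from forgetfulness it is an underdose under the protocol and a dose reduction under the SAP.

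At stake is the meaning of the exposure tables: patients with at least one reduction, the breakdown by number of reductions (1, 2, 3, or 4 and more), and the matching escalation table. A reader would take these as prescribed changes.

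**Working it through.** **Inputs.** Planned axitinib, SAP 6.5.3: "Axitinib administered BID PO at a dose of 5 mg". Planned sunitinib, SAP 6.5.3: "Sunitinib administered 50 mg PO QD on Schedule 4/2". Dose-level and counting rules: SAP 6.5.3.2 to 6.5.3.6.

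**Step 1: the plan's own figures.** Intended sunitinib dose per six-week cycle is 7 × 50 × 4 = 1,400 mg, which matches SAP 6.5.3.3. The axitinib denominator in 6.5.3.2 is 7 × 2 × 5 = 70 mg per week, and 70 / 7 = 10 mg per day. The planned daily levels are therefore 10 mg (axitinib) and 50 mg (sunitinib, on dosing days).

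**Step 2: the rules applied to single days at the planned dose.**

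| Day | Amount taken | SAP class |
|---|---|---|
| Axitinib, one of two doses skipped | 5 mg | reduction |
| Axitinib, both doses skipped | 0 mg | interruption |
| Axitinib, one extra 5 mg tablet | 15 mg | escalation |
| Sunitinib, the one dose skipped | 0 mg | interruption |

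**Step 3: titrated patients.** The SAP does not say whether the reference stays at 10 mg/day or moves with the patient's current dose. With a fixed 10 mg/day reference:

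| Prescribed | Full day | One dose skipped | One extra dose |
|---|---|---|---|
| 10 mg BID | 20, escalation | 10, as planned | 30, escalation |
| 7 mg BID | 14, escalation | 7, reduction | 21, escalation |
| 3 mg BID | 6, reduction | 3, reduction | 9, reduction |
| 2 mg BID | 4, reduction | 2, reduction | 6, reduction |

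So at 10 mg BID a skipped dose is not flagged, and at 3 or 2 mg BID an extra dose is not an escalation. If the reference is the current dose, a skipped dose is always half of it (a reduction) and an extra dose always one and a half times it (an escalation).

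**Step 4: illustrative size at 5 mg BID.** Assume that each scheduled dose is missed independently with probability p and that each day is held as its own record. A day has exactly one dose missed with probability 2p(1 − p). Over D days, P(at least one such day) = 1 − [1 − 2p(1 − p)]^D.

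| p per dose | 182 days | 365 days |
|---|---|---|
| 0.1% | 31% | 52% |
| 0.2% | 52% | 77% |
| 0.5% | 84% | 97% |
| 1% | 97% | 99.9% |

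For example, p = 0.001 gives 2 × 0.001 × 0.999 = 0.001998, and 1 − 0.998002^365 = 0.52.

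**Step 5: effect on dose intensity.** One missed 5 mg dose in a 42-day cycle leaves (420 − 5) / 420 = 98.8% of the planned amount. Relative dose intensity records the lapse at its true, small weight. The reduction count gives it the same weight as a prescribed step down.

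**The case against.** The strongest reply is that dose level is a protocol term for a prescribed step. Protocol Table 1 lists axitinib at 10, 7, 5, 3 and 2 mg BID. A 5 mg day corresponds to 2.5 mg BID and a 15 mg day to 7.5 mg BID, and neither is on the list. The patient diary in Protocol 5.2 also separates missed from changed doses. This is probably what the authors meant. However, the SAP gives its own definition in milligrams per day and does not cite Table 1 in these sections, so a programmer following it would count the lapse.

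Other parts of the reply stand:

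- A reader might infer that the misclassification occurs whichever reference dose is used. It does not: Step 3 shows exceptions for titrated patients under a fixed reference.
- A reader might infer that tolerability can no longer be compared between arms. The documents do not support that. Tables of adverse events leading to dose reduction use the recorded action taken (SAP 6.6.1 and 6.6.1.2). The toxicity endpoints are adverse events and discontinuation or failure due to toxicity. No between-arm test of the 6.5.3.4 to 6.5.3.6 tables is planned, and escalation applies to axitinib only.
- A reader might take the percentages as a forecast. The documents give no miss rate and do not show the layout of the exposure CRF. Section 6.5.3.4 also has no rule for counting repeated days, so how many patients would reach the row for four or more reductions cannot be derived without adding one.

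**Conclusion.** The point holds as a defect in a stated rule, confined to the descriptive exposure tables. Taken literally at 5 mg BID, the SAP counts one skipped axitinib dose as a reduction, one extra 5 mg tablet as an escalation, and one skipped sunitinib dose as an interruption. For titrated patients the result also depends on a reference dose that the SAP leaves open. Cumulative dose, relative dose intensity, the adverse-event-based reduction tables and efficacy are unaffected.

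The likely size is unknown. The range in Step 4 shows only that, because one day is enough to enter the table, even a very low miss rate could flag a large share of patients. It rests on assumed miss rates, independence between doses and one record per day.

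**What to change.** In SAP 6.5.3.4 and 6.5.3.5:

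1. Count axitinib and sunitinib reductions, and axitinib escalations, from changes in the prescribed dose level as listed in Protocol Tables 1 and 2. If the CRF has no prescribed-dose field, exclude days whose recorded reason is a missed, vomited or extra dose or a dosing error.
2. State whether the reference after titration is the protocol starting dose or the patient's current prescribed dose.
3. Report single missed or extra doses separately and in the same way in both arms. Keep the milligrams actually taken for cumulative dose and dose intensity.

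The cost is SAP wording, a little extra programming, and a check of which CRF fields exist. The interruption rule in 6.5.3.6 implies that reasons are collected, but neither document shows a prescribed-dose field. Nothing changes for patients.
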